2.0 Objectives*

Aims: We will conduct a comparative effectiveness trial (CET) of Couples HIV Testing and Counseling (CHTC) for adolescent-age (15-24 years) same-sex male couples. This design tests the added benefits of adjunct intervention components delivered prior to receipt of CHTC-Assertive Communication Training (ACT) videos viewed by the couple separately and individually delivered Motivational Interviewing-based Communication Skills Training (MI-CST). These target the development of communication skills necessary to participate fully in HIV prevention and sexual safety discussions inherent to CHTC. This project will assess a continuum of intervention packages to address the developmental needs of YMSM (CHTC; ACT videos + CHTC; MI-CST + ACT videos + CHTC) to identify which package optimizes outcomes while minimizing delivery cost.

Aim 1: Conduct a sequence of randomized control trials (RCTs) to evaluate the acceptability, feasibility, and comparative effectiveness of novel treatment packages.

Aim 1a: In study Phase 2, we will conduct a pilot RCT to evaluate the acceptability and feasibility of adjunct intervention components. This initial trial will recruit n=36 couples who will be randomized to one of 3 conditions: Condition 1: CHTC (only); Condition 2: couples' joint observation of ACT videos + CHTC; Condition 3: each individual within couple receiving MI-CST + joint observation of ACT videos + CHTC. Youth will then complete follow-up assessments at 1 and 3 months post-intervention. YOUTH DO HAVE THE OPTION OF COMPLETING THE INTERVENTION ON THEIR OWN IF THEY CAN NOT GET THEIR PARTNER TO AGREE TO PARTICIPATE. During Phase 3, we will recruit 200 individuals into a CET with two conditions: Condition 1: the optimum adjunct intervention package identified in Phase 2 and Condition 2: Individual HIV Testing (IHTC) as usual. Youth in this CET will complete follow-up assessments at 1, 3, and 6 months. Youth have the choice of attending the baseline visit alone or with their partner and have the option to bring their partner in later after completing the baseline alone.

Aim 1b: Assess self-management model; we posit that assertive communication skills will mediate intervention effects at all follow-ups. In study Phases 2 and 3, we anticipate between-condition differences will be greatest among YMSM with poor baseline assertive communication.

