Aim 2: Test a sustainable model of CHTC implementation in real world adolescent HIV clinics. In line with the implementation science focus of SIU U19, we utilize the EPIS to guide our implementation strategy. We will work with SIU Analytic Core's (AC) health-economist, [name], to conduct cost-effectiveness analyses to inform implementation decision-making. In collaboration with SIU ISC, we will document provider feedback to training and intervention materials to modify materials and create training packages for broad dissemination.

We will achieve our aims over two phases of the study.

PROTOCOL TITLE:

Phase 2 (n=36 couples): involves a pilot randomized control trial (RCT) to evaluate the acceptability, feasibility, and preliminary efficacy of these adjunct components.

Phase 3 (n=200 individuals): involves a CET comparing the most promising intervention package from Phase 2, consisting of individual MI, ACT video+ a recognition survey, and CHTC, compared to individual HIV testing and counseling (IHTC) delivered as usual. Participants in either condition can come as an individual or with their partner or come first as an individual and then bring their partner. This phase is focused on Implementation and Sustainment phases of the EPIS model informed by outcome analyses, cost analyses, and feedback from youth and ATN staff.

Phase 3 has now been added to this protocol document.

Hypothesis: The primary hypothesis is that because of developing skills in self-management and assertive communication, inclusion of adjunct components will be associated with clinically significant decreases in HIV transmission risk behavior as compared with partnered YMSM who receive individual testing and counseling (only). Secondarily, we propose that these intervention effects will be mediated by assertive communication skills.

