6.0 Procedures Involved*

Enrollment and Consent: Utilizing enrollment procedures established within ATN, clinic staff will invite YMSM who present for HIV testing services the opportunity to screen. These interested index partners will complete a brief iPad eligibility screener.

For Phase 2, IF ELIGIBLE, THE SCREENER WILL RANDOMIZE THEM TO COMPLETE THE BASELINE AS A COUPLE OR AN INDIVIDUAL.

If randomized to individual, staff will schedule a baseline assessment for the invited youth. If randomized to couple, staff will schedule a baseline assessment for the invited youth at a time both they and their relationship/romantic partner are available. Partners

PROTOCOL TITLE:

will independently complete informed consent at the beginning of the baseline visit, prior to assessment following ATN-wide established protocols.

FOR PHASE 2, IF THE YOUTH IS RANDOMIZED TO COMPLETE THE BASELINE AS A COUPLE, AND THEY INDICATE THAT THEY WILL BE UNABLE TO HAVE THEIR PARTNER COME FOR THE APPOINTMENT, THEY WILL BE ALLOWED TO COME TO THE BASELINE AS AN INDIVIDUAL.

For Phase 3, study sites are given the options to deliver the intervention in-person as usual, or entirely remote delivery. This is to allow sites more flexibility surrounding COVID-19 closures and restrictions, which vary by site.

For Phase 3, index partners will be able to choose to attend their baseline appointment on their own or with their partner. While scheduling the baseline, staff will ascertain whether the participant is planning to come in alone or with their partner so they can reserve adequate time, space and resources for the appointment. Regardless of whether the index partner attends alone or with their partner, after the participant(s) complete the survey at the beginning of the baseline appointment, the index partner will be randomized to the We Test intervention or individual HIV testing (IHTC) as usual. If alone and randomized to the We Test intervention, the index partner will participate in the intervention as an individual. If both members of the couple attend and are randomized to We Test, they will participate in the intervention as a couple. If both members of the couple attend and are randomized to IHTC, they will each receive IHTC as usual. The index partner who participates as an individual (in either condition) will be offered the opportunity to bring their partner to participate in the WeTest. The partner will be enrolled into the same condition as the index partner.

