12.0 Local Number of Subjects

Phase 2: 36 Couples or 72 individuals

Phase 3: 200 individuals

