1.2 Quantitative Analysis Plan

The primary hypothesis is that due to developing skills in self-management and assertive communication, inclusion of adjunct components will be associated with clinically significant decreases in HIV transmission risk behavior (TRB) as compared to partnered YMSM who receive CHTC (only). Secondarily, we propose that these intervention effects will be mediated by assertive communication skills. As stated above, we focus on four behavioral indicators of TRB. At the individual-level, we examine: (1) number of CAS acts with a casual partner in the absence of PrEP and (2) any positive chlamydia or gonorrhea diagnoses in the absence of PrEP. At the couple-level, we will examine (3) any sex in the absence of PrEP with a primary partner who reports CAS with a casual partner; and (4) any sex in the absence of PrEP with a primary partner who receives a positive chlamydia or gonorrhea diagnosis. Any missing data and additional covariates will be informed by attrition analyses prior to primary analyses.

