1.2.2 Power Analysis

Consistent with the intervention development goals of Phase 2, we are not powered to detect significant between-condition differences in primary outcomes for that phase. Power analyses for Phase 3 were conducted based on our preliminary pilot data extracted from a similar study (R34 DA036419; PI [name]) testing adjunct CHTC components in emerging adult gay male couples aged 18-29 years. Preliminary results from the 3 month wave of data collection (the most distal available with sufficient data to estimate effects at the time of protocol paper submission) suggested that viewing ACT videos prior to CHTC was associated with a 56% decrease in the odds of CAS with a casual partner (relative to CHTC alone) among HIV negative participants not on PrEP. Of particular relevance to our mediation hypotheses, viewing ACT videos prior to CHTC was associated with a 5 to 6 point decrease in avoidant communication as measured by the Communication Patterns Questionnaire (CPQ) [54]. In turn, CPQ avoidant communication scores had a significant positive association with CAS with casual partners among HIV negative men not on PrEP ($\exp B = 1.06, p < .01$). Separately, our previous study of brief MI interventions with YMSM suggest it is associated with as much as an 83% reduction in the odds of CAS with a casual partner [55] compared to an attention-matched psychoeducation control condition.

These preliminary effect sizes were utilized as parameters in power analyses using a Monte Carlo simulation approach in Mplus (version 7.3)[53]. This approach provides a direct estimation of power while modeling both the multilevel structure of data (individuals are nested within couples) and the longitudinal design of the study (each individual provides data at 3 follow-up points). The program generates random samples from the specified population and, within each sample, examines the significance of freed parameters. Power is defined as the proportion of simulated samples in which the freed parameter has a p value of less than .05. All models specified a random seed and used 10,000 sample replications. Power analyses conducted based on these preliminary effect sizes suggests that $n = 144$ couples ($n = 288$ individuals), anticipating a minimum of $n = 232$ individuals retained at 6 months, is adequate to achieve power $> .80$ for all hypothesized direct effects as well as indirect pathways.

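### The SAP's primary hypothesis (against CHTC only) and its Phase 3 power claim describe a contrast and a sample that Phase 3 does not have

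*SAP*

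**What the plan says.** **Hypothesis.** SAP 1.2 gives a single primary hypothesis, without distinguishing phases: adding the adjunct components leads to "decreases in HIV transmission risk behavior (TRB) as compared to partnered YMSM who receive CHTC (only" condition. The hypothesis paragraph in Protocol 2.0 is nearly the same sentence with a different comparator: "as compared with partnered YMSM who receive individual testing and counseling (only" condition.

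**Arms.** A CHTC-only arm exists in Phase 2, one of its three conditions. For that phase the SAP says "we are not powered to detect significant between-condition differences in primary outcomes for that phase". Phase 3 has two arms. Protocol 2.0 describes it as "Phase 3 (n=200 individuals): involves a CET comparing the most promising intervention package from Phase 2" (individual MI, the ACT video with a recognition survey, and CHTC) with IHTC; Aim 1a lists the other arm as "Condition 2: Individual HIV Testing (IHTC) as usual". Protocol 6.0 agrees: "the index partner will be randomized to the We Test intervention or individual HIV testing (IHTC) as usual". Someone who comes alone and is allocated to We Test takes part solo: "the index partner will participate in the intervention as an individual".

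**Power and sample size.** SAP 1.2.2 (Power Analysis) is explicitly for Phase 3. Its inputs are a 56% reduction in the odds of condomless sex with a casual partner for ACT videos plus CHTC, against CHTC by itself, and a reduction of up to 83% for brief MI, against a psychoeducation control matched for attention. It concludes that 144 couples (288 individuals, at least 232 retained at 6 months) give power above .80 for every direct and indirect effect. Protocol 12.0 says "Phase 3: 200 individuals". The SAP mentions neither IHTC nor 200 individuals.

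**The concern.** The two documents state different primary hypotheses, and the SAP's version names a comparator that Phase 3 does not randomise. Package versus IHTC bundles CHTC with the adjuncts, so a difference between arms could come from CHTC, from the adjuncts, or from both. Read under the SAP's wording, a valid package effect would be reported as added benefit of communication training over CHTC. That is the question that decides which components are worth paying for, and only the unpowered Phase 2 randomises it.

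The power statement was not updated either. It rests on effects measured against two other controls, assumes that everyone is enrolled in a couple, and uses a sample 44% larger than the protocol's (288/200 = 1.44). A reader would take power above .80 as a property of the planned trial when nothing in the documents shows it.

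**Working it through.** **1. Is the SAP's contrast available in Phase 3?**

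| Source | Active side | Comparator |
|---|---|---|
| SAP 1.2 hypothesis | adjunct components | CHTC only |
| Protocol 2.0 hypothesis | adjunct components | individual testing |
| Phase 2 arms (Protocol 2.0, 6.0) | ACT + CHTC; MI-CST + ACT + CHTC | CHTC only |
| Phase 3 arms (Protocol 2.0, 6.0) | MI + ACT + CHTC package | IHTC |
| Power input 1 (SAP 1.2.2) | ACT + CHTC | CHTC only |
| Power input 2 (SAP 1.2.2) | brief MI | psychoeducation |

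The SAP hypothesis matches Phase 2 only. Neither power input matches Phase 3. The growth model in SAP 1.2.1 names no comparator, so it can validly estimate package versus IHTC; it cannot recover adjuncts versus CHTC from Phase 3 data.

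**2. The SAP's own figures.** Retention = 232/288 = 0.806, so its two sample sizes agree. The power figure cannot be reproduced exactly, because the control risk, within-couple correlation, variances and allocation are not given. A rough check uses two proportions, OR = 1 − 0.56 = 0.44, two-sided alpha .05, 1:1 allocation and no clustering (all but the OR and the .05 level are assumptions). The three-wave columns average the follow-ups with within-person correlation 0.5 (assumption).

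| Control risk (assumption) | One wave, 232 | One wave, 161 | Three waves, 232 | Three waves, 161 |
|---|---|---|---|---|
| .20 | .58 | .43 | .75 | .60 |
| .30 | .73 | .57 | .88 | .75 |
| .40 | .82 | .66 | .94 | .83 |
| .50 | .86 | .71 | .96 | .87 |

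Power above .80 at 232 is plausible for OR 0.44, but it depends on inputs that are not stated.

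**3. Same effect, protocol sample.** Retained = 200 × 0.806 = 161; 161/232 = 0.694, or 31% fewer. This takes the 200 as everyone enrolled. Rescaling the SAP's claim needs no control risk:

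power at 161 = Φ[(1.96 + z(P0)) × √(161/232) − 1.96], where P0 is the power at 232.

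- P0 = .80: Φ(2.802 × 0.833 − 1.96) = Φ(0.374) = .65
- P0 = .90: Φ(3.242 × 0.833 − 1.96) = Φ(0.740) = .77
- P0 = .95: Φ(3.605 × 0.833 − 1.96) = Φ(1.043) = .85
- P0 needed to keep .80 at 161: Φ(2.802 × √(232/161) − 1.96) = Φ(1.403) = .92

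**4. Solo attendance.** Take a design effect of 1 + ICC for paired participants and 1 for solo participants (assumption), with the 288 plan all paired. If everyone attends solo, the ratio 161/232 is multiplied by 1 + ICC. From P0 = .80, power at 161 is .65 if all are paired, whatever the ICC. If all are solo it is .72 at ICC 0.2, .79 at ICC 0.4 and .82 at ICC 0.5.

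**5. Different effect.** Anchor .80 at 232 for OR 0.44 (assumption) and scale the noncentrality by ln(OR)/ln(0.44). Power at 161:

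- OR 0.17 (the 83% input): above .99
- OR 0.44 (the 56% input): .65
- OR 0.60 (assumption, no source in the documents): .31
- OR that keeps .80: 0.44^√(232/161) = 0.44^1.200 = 0.37

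The assumed effect matters more than the sample size, and the documents give none for We Test versus IHTC.

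**The case against.** The strongest reply is that the planned model still estimates the right Phase 3 effect and the protocol already states the IHTC hypothesis, so this is outdated wording and a misreading is unlikely. The first part stands: the estimator is sound. But the SAP is the document that fixes what a positive result may claim, and it names the wrong comparator. Protocol 2.0 does not fully prevent the misreading, because it too credits the effect to including adjunct components.

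The second reply is that power could be adequate. This also stands as far as it goes. The SAP claims more than .80, so .80 is a floor; from .95 the result at 161 is .85. Solo attendance with a within-couple correlation of about 0.44 or more would restore .80 in the extreme case where nobody is paired. The full package against IHTC could have a larger effect than ACT videos alone against CHTC, and OR 0.37 would be enough. These points rule out saying that Phase 3 is underpowered. They do not supply the missing justification.

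Third, the 200 might count index partners only, since Protocol 6.0 randomises the index partner and lets the partner join the same condition. If all 200 brought partners, 400 × 0.806 = 322 would be retained, and power on the same anchor would be about .91. That reading sits poorly with Protocol 12.0, which counts individuals, and it would still not be the SAP's 144-couple design.

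Finally, Protocol 24.0 still names standard CHTC as the later trial's comparator. That section also describes the study as being in Phase 2; Protocol 2.0 and 6.0 define the Phase 3 arms.

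**Conclusion.** The concern holds. Phase 3 has no CHTC-only arm, so it cannot test the primary hypothesis in SAP 1.2, and the SAP and protocol disagree on what that hypothesis is. This part needs no assumption.

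The power claim does not carry over to Phase 3, because its effect inputs come from other contrasts and its 288 individuals exceed the protocol's 200. If the 200 are all participants and the SAP's retention applies, a power of .80 falls to about .65 for the same effect with everyone paired, and .90 falls to about .77. Those figures depend on the anchor, the mix of solo and paired participants, and who the 200 are. The conclusion is that Phase 3 power is undetermined and not shown to exceed .80; it has not been shown to be too low. Because the primary hypothesis governs the trial's main claim, this must be fixed before analysis.

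**What to change.** - **SAP 1.2:** write one hypothesis per phase. Phase 2: adjuncts plus CHTC versus CHTC only, descriptive and unpowered. Phase 3: the full We Test package versus IHTC as usual, across participants attending alone and as couples, with a statement that the effect will not be attributed to the adjuncts over CHTC.
- **Protocol 2.0:** reword the hypothesis so that it refers to the package and not to the inclusion of adjuncts.
- **Protocol 24.0:** correct the leftover CHTC comparator.
- **SAP 1.2.2 (Power Analysis):** either justify an assumed effect for We Test versus IHTC and rerun the Monte Carlo simulation at 200 individuals, or withdraw the claim of power above .80 for Phase 3. A rerun should state whether the 200 include partners, the expected solo/couple mix, retention, control risk and within-couple correlation.

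The cost is a few sentences in two documents and one simulation rerun, or none if the claim is withdrawn. The Phase 3 claim narrows to a package effect. Trial conduct does not change unless the rerun leads the sponsor to revisit the sample size.

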1.2.1 Analytic Plan

All primary outcome variables will be tested in the context of a multilevel growth model, which accounts for the nesting of individuals within couples. In order to capture within-individual change over time, we will utilize a latent growth curve approach to modeling follow-up data. At the individual level (Level I), models will include an intercept and linear slope component to represent the initial value and change over time in each participant's outcome. We will explore the inclusion of quadratic components as indicated by model fit. Mplus provides the flexibility to accommodate count and dichotomous outcomes. Growth factors will then be regressed on intervention condition at the couple level (Level II) and the effect of the intervention will be evaluated by examining the regression coefficient (and associated *p* value) associated with intervention condition for each of these factors.

Secondary analyses of individually reported self-management and dyadic functioning as potential mediators of the intervention's effect on TRB will specify growth factors for self-management, dyadic functioning, and communication skill scores during the follow-up period. In this manner, growth factors for the outcome can be regressed on growth factors for the putative mediator. Intervention effects (a couple-level predictor) will be determined by examining regression coefficients associated with intervention in the prediction of growth factors for both

the outcome of interest and mediator. For significant direct effects, indirect path from intervention communication will be tested using bootstrapping tests of mediation. Where outcome distributions prevent bootstrapping, we will utilize a model constraint approach to evaluate significance of indirect effects. The product of constituent direct effects is constrained as zero. The overall model fit under this constraint is compared to one where the constraint is not specified. A statistically significant reduction in fit associated with constraint represents evidence that indirect effects differ from zero[53].

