5.0 Study Intervention

Intervention Design and Procedures: The primary innovation of this multilevel CET lies in the novel packaging of existing interventions in a manner that addresses the

PROTOCOL TITLE:

specific developmental needs of YMSM. While MI-CST, video based ACT, and CHTC have individually established efficacy, this study will be the first to evaluate a continuum of prevention packages, which combine these components. In addition, this multilevel intervention seeks to leverage the power of the dyadic processes to enhance motivation for HIV testing and prevention (including biomedical prevention). Our adjunctive components (ACT and MI-CST) are specifically intended to enhance self-management skills (e.g., assertive communication) which are essential to effectively engage relationship partners in collaborative sexual goal development and problem solving. The underlying assumption of this strategy is that improvements in dyadic functioning will lead to reductions in sexual risk for both individuals within the relationship. Finally, we make innovative use of biomarkers to operationalize HIV-transmission risk. Our ability to draw conclusion about intervention effects is enhanced by examining biomedical and behavioral outcomes for both sexual partners regardless of relationship dissolution; this is critical to enhance sexual safety for both individuals of a couple, particularly in light of the short duration and rapid re-partnering of YMSM during this developmental period.

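### Phase 3 partners who enrol after the index partner is randomised enter the primary comparison by default, because the SAP defines no analysis set and does not flag them

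*SAP*

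**What the plan says.** Protocol 2.0 (Aim 1a) lets Phase 3 youth attend baseline alone or with a partner, and they "have the option to bring their partner in later after completing the baseline alone". The Phase 3 paragraph of the same section says that participants in either condition may "come first as an individual and then bring their partner". Protocol 6.0 adds the mechanics. The index partner is randomised after the baseline survey. One who took part alone, in either arm, is offered the chance to bring a partner, and that partner is placed in the index partner's arm. Randomisation is stratified by, among other factors, individual or couple attendance.

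SAP 1.2.1 states: "All primary outcome variables will be tested in the context of a multilevel growth model, which accounts for the nesting of individuals within couples". Condition is a couple-level predictor of the growth factors, and the intervention effect is read from the coefficient "associated with intervention condition for each of these factors". SAP 1.2 lists four outcomes. Outcomes 1 and 2 are individual: casual-partner condomless acts and STI diagnoses, each without PrEP. Outcomes 3 and 4 need the primary partner's own report or test result. Outcome 3, for example, is "any sex in the absence of PrEP with a primary partner who reports CAS with a casual partner".

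The SAP text available for review has no analysis-set definition, no late-partner indicator and no sensitivity analysis for late partners. The discontinuation table in Protocol 14.0 sets denominators for withdrawal, ineligibility and death only.

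**The concern.** A late partner is not randomised. He joins after allocation, into an arm that the index partner has already experienced, and no blinding is described. One arm contains couples counselling and the other is individual testing as usual, so the arm could affect who brings a partner and which partners come. If it does, the people analysed differ between arms for reasons other than treatment effect, and a larger sample does not remove the difference.

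For outcomes 3 and 4, late entry also decides for which index partners the outcome can be fully determined. Leaving late partners out does not cure that.

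The missing-data methods in the SAP's Equivalency Tests section do not settle the matter. Attrition models, full-information maximum likelihood and missingness models deal with missing values of enrolled participants, not with who belongs in the comparison. The baseline balance tests in that section could partly reveal an imbalance caused by late partners, but would not correct it.

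**Working it through.** **The plan's own figure.** SAP 1.2.2 (Power Analysis) states power above .80 for 288 individuals with 232 retained (232/288 = 80.6%). Base rate, within-couple correlation and growth variances are not given, so the figure can be neither confirmed nor refuted. It does not decide this point, which is about who is analysed.

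**Assumed inputs.** The documents give none of these: f = share of index partners attending jointly; u = late uptake among those attending alone; index risk 40%; partner risk r = 20% or 50%; no true effect.

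**Step 1. Outcomes 1 and 2, dichotomised, one time point.** Risk per arm = [0.4 + (f + (1−f)u)r] / [1 + f + (1−f)u], with u = 0.5 versus 0.1.

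| f | r = 20% | OR | r = 50% | OR |
|---|---|---|---|---|
| 0.25 | .323 vs .351 | 0.88 | .438 vs .425 | 1.06 |
| 0.50 | .314 vs .329 | 0.93 | .443 vs .435 | 1.03 |
| 0.75 | .307 vs .313 | 0.97 | .447 vs .444 | 1.01 |

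With equal uptake, or r = 40%, the OR is 1.00. Joint and late partners share the same r in both arms, so within each role the arms are identical. These departures reflect only the mix of index partners and partners, and an index/partner term removes them. Using a rough SE(log OR) of 0.427 for 200 individuals (step 5), an OR of 0.93 is |ln 0.93|/0.427 = 0.17 SE, giving a type I error of about 5.3%; an OR of 0.88 gives about 6.0%.

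**Step 2. Repeated measures.** A simplified three-wave logistic model was fitted with no partner term, with couple and person random-intercept variances of 0.6 and 0.8 and no random slope. It puts the shift on the intercept (OR 0.85 to 1.08 over the same cases), with slope OR 1.00. The largest shift implies a type I error of about 6.7%. If late partners are placed on the index partner's clock and miss the 1-month wave, part of the shift moves to the slope (0.990 per month at f = 0.5, r = 20%).

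**Step 3. Late-partner risk that differs by arm.** Assumed: index risk 30%, no joint partners, no true effect on index partners. Risk per arm = (0.3 + u × r)/(1 + u).

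| Uptake | Late-partner risk | Pooled risk | OR | Type I error, 70 index per arm (182 people) |
|---|---|---|---|---|
| 30% vs 30% | 20% vs 30% | .277 vs .300 | 0.89 | 6.4% |
| 40% vs 20% | 20% vs 30% | .271 vs .300 | 0.87 | 7.1% |
| 50% vs 10% | 15% vs 30% | .250 vs .300 | 0.78 | 11.5% |

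Here the arms differ within the partner role, so an index/partner term is no cure. Leaving late partners out returns the OR to 1.00.

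**Step 4. Outcomes 3 and 4, index partners with an enrolled partner.** Risk is 30% in joint couples and q = 20% or 40% in late-formed couples. Risk per arm = [0.3f + (1−f)uq] / [f + (1−f)u], with u = 0.5 versus 0.1. At f = 0.25, 0.50 and 0.75 the ORs are 0.82/1.18, 0.89/1.12 and 0.95/1.05.

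Scoring an unenrolled partner as no event is worse. At f = 0.5 with 30% risk in every couple, the scored risks are 0.75 × 0.3 = .225 and 0.55 × 0.3 = .165. The OR is (.225/.775)/(.165/.835) = 1.47 with no true effect.

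**Step 5. Cost.** Assume that late partners count within the 200 and that u = 0.3. Index partners = 200/[2f + (1−f)(1.3)] = 135.6, 121.2, 109.6. Late partners = index × (1−f) × 0.3 = 30.5, 18.2, 8.2. Joint couples = index × f = 33.9, 60.6, 82.2. Individuals with an enrolled partner = 2 × (joint couples + late partners) = 129, 158, 181.

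Rough power uses OR 0.44 (the SAP's figure for casual-partner acts, borrowed here), control risk 30% (so .159 treated), ICC 0.2 and n per arm = individuals × .806/2/1.2.

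| f | Couple stratum: SE, power | All with an enrolled partner: SE, power |
|---|---|---|
| 0.25 | .734, 0.20 | .532, 0.34 |
| 0.50 | .549, 0.32 | .481, 0.40 |
| 0.75 | .471, 0.41 | .449, 0.45 |

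**The case against.** The strongest reply is that the calculated effect for outcomes 1 and 2 is slight, is a matter of role mix, and can be met by an index/partner term without dropping anyone. That stands for step 1. It fails for step 3, and nobody can know in advance which case applies.

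A second reply is that the SAP was plainly not revised for Phase 3: it still names a CHTC-only comparator and 144 couples, while the protocol has individual testing and 200 individuals. Silence on late partners is one symptom. That is fair, and it makes the omission easy to explain, but the rule is still needed.

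A third is that Protocol 5.0 stresses examining "outcomes for both sexual partners regardless of relationship dissolution", so moving late partners out of the primary set works against an aim of the study. Keeping them in a pre-specified secondary analysis answers most of this.

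A reader might also infer that the SAP orders pooling. It does not; pooling is the default reading because nobody is excluded. Nor do the documents support inferring that uptake does differ by arm, since they give no uptake data.

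Finally, it is tempting to set the couple stratum's power against that of all 200 (about 0.48). That comparison is wrong, because outcomes 3 and 4 are not fully determinable for participants without an enrolled partner.

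**Conclusion.** The gap is real and worth fixing. As written, the plan lets people selected after allocation into the randomised comparison, with nothing to identify them. The bias requires late uptake or late-partner risk to differ by arm, and it disappears when uptake and late-partner risk are equal across arms. Every magnitude above rests on assumed inputs and on models simpler than the SAP's; outcome 1, for instance, is a count.

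It would go too far to say that the randomised comparison as a whole is compromised. Index partners and couples who attend together are fixed before randomisation, so comparisons limited to them are protected at entry. The role-mix effect is also modest beside the SAP's planning effect of 56% lower odds.

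Confidence is moderate. For outcomes 3 and 4 it is lower, because SAP 1.2 refers back to an outcome description that is not in the text available for review and may say more about how partner data are obtained.

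**What to change.** 1. Before outcome data are compared by arm, define the primary analysis set for outcomes 1 and 2 as randomised index partners plus partners who completed baseline before randomisation. Analyse late partners in a pre-specified secondary or sensitivity analysis with an index/partner term, and state when their follow-up clock starts.
2. For outcomes 3 and 4, present a by-arm comparison in the stratum that attended as a couple, described as protected at entry but imprecise and as answering a narrower question. In any analysis of all index partners, do not score an unenrolled partner as no event; treat the outcome as missing and vary the assumption.
3. Report late-partner enrolment by arm, and state whether late partners count towards the 200.
4. Separately, reconcile the inclusion criterion in Protocol 10.0 that both partners agree to attend an assessment together with the solo and late-partner routes in Protocol 2.0 and 6.0.

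The cost is SAP text plus each partner's enrolment date relative to randomisation, which the documents do not confirm is recorded. About 8 to 31 of 200 participants leave the primary set (75% to 25% joint attendance, on the step 5 assumptions). For outcomes 3 and 4, restricting to the couple stratum gives up the power shown in the step 5 table, most of it when joint attendance is low.
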